[figure not shown]

## **Overview of Study**

### **Background**

Traumatic spinal injury (TSI) accounts for a significant proportion of disability and death worldwide, with the majority of this burden affecting individuals in low- to middle- income countries. Crucially, to date, the current disease profile of TSI has not been characterised globally. In addition, the global approach to the care of patients following TSI is inconsistent with considerable geographical differences in process of care reported, and limited data available on the impact of these variations on outcomes following TSI. A better understanding of case-mix and processes of care is urgently needed to underpin efforts to identify ways of improving outcome relevant to different socioeconomic settings globally.

### **Objectives**

The primary objective of this study is to characterise the case-mix, processes of care and variations in non-operative and operative management strategies, including emergency, ward, ICU care, in patients presenting with traumatic spinal injury (TSI) between centres across low and high Human Development Index (HDI) countries. The secondary aims are to summarise current local resources and management pathways for TSI through validation of provider profiling data, describe differences in indications for nonoperative and operative management, and short-term outcomes following TSI. This study aims to identify gaps in processes of care to identify targets for future interventions to improve TSI care across high and low-resource settings.

### **Methods**

A multi-centre, international, prospective, observational study. Any unit assessing patients with TSI worldwide will be eligible to participate. Each participating unit will form a study team responsible for gaining local approval, identifying patients for inclusion and conducting data collection. Data will be collected via a secure online platform in an anonymised form. Processes of care will be characterised by a detailed provider profiling exercise. A registry describing the case-mix and care of all adults presenting with radiologically confirmed TSI will be collected, in a given consecutive 30-day period during the study period starting in 2021.

### **Results**

The dataset, developed through an iterative feedback process involving clinicians from low and high Human Development Index (HDI) countries, includes patient demographics, details of injury mechanism, local injury management and, if applicable, timing and nature of surgery, post-operative care and immediate post-operative complications. Outcome measures include Frankel grade at 6 weeks post-admission (or at discharge or death, whichever event occurs first), early mortality, peri-operative complications, adverse events of special interest, functional status and mobility. Descriptive analyses of case-mix and the variations

in processes of care will be conducted. Available resources, use of guidelines and variations in processes of care will be characterised using both provider profiling responses and patient-level data collected. Areas where known best practice is deficient or unavailable will be identified as potential targets for future implementation studies.

### **Conclusions**

GNOS Spine aims to provide a global snapshot of the case-mix, management, processes of care and short-term outcomes of patients presenting with TSI. In addition, we aim to identify areas for further study, and establish a platform and clinical network to facilitate this future research in global neurotrauma and spinal surgery.

## Background

Traumatic spinal injury (TSI) is an umbrella term for injuries to the spinal cord, nerve roots, osseous structures, and disco-ligamentous components of the spinal column. Traumatic spinal cord injury (SCI) is a subset of TSI which is most commonly reported in literature. TSI represents a significant global disease burden, recently reported to be 1.6 times higher in low- to middle-income countries (LMICs) than high-income countries (HICs). Furthermore, ongoing indirect costs of severe disability secondary to TSI are a recognised socioeconomic burden, which may disproportionately affect LMICs.

### *Management of traumatic spinal injury (TSI)*

Delays in the initiation of comprehensive management of TSI have been shown to add to the complexity of management, result in a higher incidence of complications, longer hospitalisation, added costs and poor outcomes. The Lancet Commission on Global Surgery estimates that 5 billion people worldwide lack access to safe, affordable, accessible surgical care and this disparity extends to neurosurgical interventions. Challenges to delivering emergency management of TSI in LMICs are often compounded by inadequate pre-hospital care, lack of infrastructure and trained manpower.

### *Neurosurgical research in low- to middle-income countries (LMICs)*

Whilst the epidemiology of TSI has been described in a number of LMICs, there is limited literature describing current practice for the management of TSI in resource-limited settings. Additionally, a 2011 bibliometric review of all neurosurgical publications over 13 years found that in almost 70% of all published work the first author originated from one of only 5 high or upper-middle income countries. The limited resources that clinicians work within in LMICs presents a challenge to adhere to latest practice guidelines that are developed in high-income countries (HICs). The discrepancy between management and available resources urges a need for up-to-date, context-specific clinical data collected directly from these countries to allow a better understanding of current practice, and future TSI guidelines to be tailored to the specific capabilities of the country. Variances in processes of care have even been identified between centres in HDI settings and are likely to be substantial at all stages of TSI care, including pre-hospital, emergency department, ward-based, operative and ICU phases. Characterisation of these variances may offer important opportunities to intervene across both high and low-resource settings.

### *Conclusion*

We propose to conduct an international, multi-centre, prospective, observational study of outcomes following admissions for TSI. We believe this project will provide valuable insight into current practice to identify areas for future studies and establish a platform and clinical network to facilitate this future research in global neurotrauma and spinal surgery.

## **1. Objectives**

[figure not shown]
### **1.1 Primary Objective**

- Characterise case-mix, processes of care and variations in nonoperative and operative management strategies, including emergency, ward, surgical and ICU care, in patients presenting with traumatic spinal injury (TSI) between centres across low and high Human Development Index (HDI) countries

### **1.2 Secondary Objectives**

- Summarise the current resources and management pathways for patients presenting with suspected traumatic spinal injury worldwide, through validation of provider profiling data
- Describe differences in current (i) indications for conservative management vs surgery, and (ii) short-term outcomes (early mortality, functional, neurological, adverse events) following TSI worldwide.
- Identify gaps in implementation of current evidence-based best practice and explore possible reasons in specific settings.
- Identify targets for future global health, process of care or clinical interventions to improve outcomes across different settings.
- Obtain point-estimates of, and gain insights into local variations in the epidemiology of TSI.
- Define patient profiles which predict efficacy of specific interventions and pathways of care.
- Identify possible performance indicators to characterise TSI care across settings in preparation for a future consensus study.

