### 3.5 Study measures

The following categories of routine clinical data will be collected prospectively for all patients included in the study. The full data set is included in *Appendix A*.

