#### Injury management data

- Intended injury management
- Injury management during transfer e.g. immobilisation
- Specialised therapies received e.g. physiotherapy, speech and language therapy

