## **5. Statistical Analysis**

Anonymised data will be analysed by the central study team. Fundamentally the main analysis will consist of a quantitative description of case-mix and the variations in processes of care. Identification and description of areas where known best practice is lacking or unavailable will be performed. This will enable identification of potential targets for future implementation studies.

In addition, early outcomes will be assessed to identify case-mix and process factors that may form a substrate for intervention. Participating centres will be stratified based on their country into groups based on their Human Development Index (HDI). The Human Development Index is calculated for each country based on its life expectancy at birth, years of schooling and gross national income (GNI) per capita.

Specifically, after data validation and curation, the primary analysis will comprise of (1) statistical descriptive analysis of patient-level registry variables, (2) characterisation of processes of care using statistical descriptions of both provider profiling data and patient-level process variables followed by a description of typical process groupings. This will follow and extend methodologies that have previously been applied successfully to traumatic brain injury. Case-mix and process analysis will be stratified in a nested way by site, country, and association with human development index (HDI).

Analysis for the secondary objectives will consist of a quantitative statistical summary of non-operative and operative management. Intra- and inter-site variances will be compared and associations with HDI and process of care factors sought.

Whilst only short-term outcomes can be obtained in this pragmatic point-study, outcomes analysis will be attempted for early mortality, functional status as assessed using the 5-point Frankel Grade, neurology, adverse events and trajectory from admission to 6 weeks post-injury (or discharge or death, whichever occurs first). These will be analysed by HDI group in an appropriate nested model accounting for random effects of site and country. Either ordinal models (for statistical power) or dichotomised models will be used depending on the statistical properties of the data and suitability of model assumptions. Mixed effects models will be used to assess the relationship between HDI and deterioration in functional status at 6 weeks while controlling for confounding variables.

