## **6. Limitations**

This pragmatic, prospective, observational study has been designed with the aim of obtaining estimates of the current global case-mix, management and processes of care for patients who present with TSI at a single point in time. Long-term follow-up is therefore not appropriate or feasible across all settings. This protocol has not been designed to investigate or provide:

- Worldwide epidemiological data of all TSI
- Indications for or efficacy of specific management for patients with TSI
- Long-term outcomes following TSI

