**10.3 Injury Management**

What was the intended injury management?	
 
● No intervention
 
● Non-operative
 
● Operative
 

Was there immobilisation during transfer?	
 
● Nothing
 
● Collar
 
● Trauma board
 
● Bed
 

Did the patient have surgical bedrest?	
 
● Nothing
 
● Bedrest, no logroll
 
● Bedrest + logroll
 
● Collar only
 

Traction?	
 
● Yes
 
● No
 

Did the patient receive any specialist therapy as an inpatient	
Yes No
 
If Yes, what type of therapy was provided?
 
 
- Speech and Language Therapy
 
- Tracheostomy care
 
- Physiotherapy
 
- Occupational therapy
 
- Alternative therapy – Ayurveda etc
 
- Other (specify _____)
 

Was spinal surgery performed?	
 
● Yes, performed at this institution
 
● Yes, transferred to a different institution for surgery
 
● No
 

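### Objective 1.2(i) promises to describe indications for conservative management versus surgery, but Section 6 disclaims indications and no registry field records a reason

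*Combined protocol and SAP*

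**What the plan says.** The overview gives as a secondary aim to "describe differences in indications for nonoperative and operative management", and Section 1.2 repeats it as item (i) of its second bullet: "Describe differences in current (i) indications for conservative management vs surgery".

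For data, Section 3.5 lists "Intended injury management" among the management variables. Of Appendix A it states: "The full data set is included in" that appendix. Field group 10.3 asks what management was intended (no intervention, non-operative or operative) and whether spinal surgery took place (at this institution, after transfer elsewhere, or not).

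For analysis, Section 5 states: "Analysis for the secondary objectives will consist of a quantitative statistical summary of non-operative and operative management". It adds comparisons within and between sites and a search for associations with HDI and process factors. It does not mention indications.

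Section 6, in its list of what the protocol was not designed to investigate or provide, includes "Indications for or efficacy of specific management for patients with TSI".

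**The concern.** An indication is the reason for a decision. To describe how indications differ between settings, the study needs either a recorded reason or a stated rule for deriving one from other fields. The plan has neither, and its own limitations section disclaims the subject.

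This matters because of the comparison the study is built on. The background rests on unequal access to surgery and limited resources, and the objectives aim to find targets for intervention across high- and low-resource settings. For that purpose, a patient managed conservatively because surgery was judged unnecessary is a different finding from a patient with a similar injury who went without surgery because it could not be paid for, staffed or equipped. If a lower operation rate in one HDI group is reported as a difference in indications, clinical judgement and access are mixed. The mixing is likely to be greatest where resources are shortest. The data are anonymised and mostly fixed-option, so the reason cannot be reliably reconstructed afterwards.

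**Working it through.** The plan has no figure to reproduce, and the point depends on no sample size or error rate. The check is a reading of every Appendix A field against the objective.

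**1. Is the field list complete?** Section 3.5 says so. A field absent from Appendix A is therefore absent from the registry as planned.

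**2. What each field group offers**

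| Field group | Relevant content | Reason for the management choice? |
|---|---|---|
| 10.1 Injury and admission | Initial Frankel grade, deformity, other injuries | No |
| 10.2 Imaging | AO class, subluxation/translation; disc herniation with cord compression and haematoma when imaging goes beyond plain film | No |
| 10.3 Management | Intended management; surgery performed | No: the choice, not the reason |
| 10.4 Operative | How surgery was done, funding, optional comment on the procedure | No |
| 10.5 Outcome | Outcomes, complications, return to theatre | No |

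Fields recording the choice: 2. Fields recording a reason for it: 0.

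**3. Could 10.4 fill the gap?** No. It opens only when surgery was performed at the reporting institution. Its funding item and its comment field therefore do not exist for unoperated patients, and these are the patients in question.

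**4. What the two choice fields give.** Three options for intention by three for performance make 3 × 3 = 9 combinations. One of them, operative intended with surgery not performed, marks planned surgery that was not delivered and can be tabulated by HDI group. Its cause is not asked. In the two combinations where no intervention or non-operative management was intended and no surgery followed, clinical choice and lack of access can be entered alike. Intention is not defined on the form, so a clinician who already knows surgery is unavailable may enter non-operative. The documents do not show how often that would happen.

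**5. Could provider profiling fill the gap?** Section 3.2 describes one questionnaire per institution, completed before patient-level collection begins, on caseload, catchment, frameworks and resources. It can show that a site lacks a resource. It cannot show which patient went without surgery for that reason. The questionnaire is not reproduced, so whether it asks about local indications is unknown.

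**6. Objective against limitation.** The overview and Section 1.2 say indications will be described. Section 6 says the protocol was not designed to investigate them. All three are current text.

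**The case against.** The strongest reply is that the registry holds more than this point might suggest. AO class, subluxation/translation, deformity and initial Frankel grade are part of the form for every patient. Intended and performed management are separate fields, so undelivered surgery is visible. Profiling covers resources from pre-hospital care through to intensive care. Section 5 plans to relate profiling to best practice, process of care, case-mix, site and HDI. Describing the features of patients who were and were not operated on is a legitimate way to study treatment decisions.

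Most of this stands, and it rules out three stronger readings:

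- A reader might infer that a stable injury managed conservatively by choice and an unstable injury left unoperated look the same in the data. They usually would not, because the injury fields would differ. The ambiguity is confined to patients with similar recorded injuries.
- A reader might infer that the study will yield only operation counts by HDI group. Section 5 plans more than that.
- A reader might infer that the study as a whole has no route to reasons for gaps in care. The separate objective on gaps speaks of reasons in settings, and site-level profiling is a planned route to it.

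One could also read the Section 6 bullet as disclaiming only what the indications ought to be, leaving description of current indications in scope. The text does not draw that distinction, and on that reading the reason field is still missing.

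What does not stand is that correlates answer the objective. The features that accompany surgery form a treatment pattern. Calling that pattern an indication assumes that access plays no part in the decision, and the study's own rationale says access is unequal.

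**Conclusion.** The point holds in a bounded form. The objective and the limitation contradict each other, and with 2 fields for the choice and 0 for the reason, objective 1.2(i) as worded cannot be answered from the patient registry. Treatment patterns by injury feature and counts of undelivered planned surgery can be reported. Two things cannot be recovered: the reason for non-operation among patients with similar injuries, and the reason planned surgery was not performed.

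The effect on any HDI comparison cannot be sized. The documents give no operation rates and no share of decisions driven by access, so any percentage would be invention. The conclusion rests on Appendix A being complete, as Section 3.5 states, and is limited to the patient registry because the profiling questionnaire is not shown.

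This should be corrected. One secondary objective is affected; the primary descriptive objective is not.

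**What to change.** Preferred change:

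- Add to 10.3, for every patient and completed when the decision is made, one fixed-option, select-all item: *Main reason(s) for the intended management*. The options should separate clinical reasons (for example neurological deficit, instability or deformity, stable injury, unfit) from refusal by patient or family, cost, no implants or equipment, no surgeon or theatre, and other.
- Add a conditional item, *Reason not performed*, shown only where operative management was intended and surgery was not performed.
- State in Section 5 that both will be reported by site and HDI group under objective 1.2(i), and amend the Section 6 bullet to match.

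If the form is locked, reword objective 1.2(i) and the overview to *describe the patient and injury characteristics of those managed with and without surgery*, so that they agree with Section 6.

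The first route costs slightly longer data entry and possible local re-approval of the changed form. The reasons would be clinician-reported and somewhat subjective. The second is a wording change and gives up the claim to describe indications. Both are changes to data collection or wording, and neither alters how any patient is managed.

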## 2. Overview – Study Flowchart

### **3. Methods**

#### **3.1 Inclusion Criteria**

##### **3.1.1 Centre inclusion Criteria**

Any primary, secondary or tertiary institution worldwide managing patients with TSI is eligible to participate. In many institutions, management for TSI may be provided by spinal surgeons – however, centres in which management for TSI is provided by general surgeons, trauma surgeons, general medical doctors or even non-physician clinicians are also eligible to participate.

##### **3.1.2 Patient inclusion and exclusion criteria**

###### **3.1.2.1 Inclusion Criteria**

All adult patients presenting to the participating institution with a first presentation of TSI confirmed radiographically, during the selected 30-day inclusion period are eligible for inclusion in the core study.

###### **3.1.2.2 Exclusion Criteria**

- Elective (planned) or semi-elective (patient initially discharged after emergency with planned intervention at a future date) admissions
- Patients who have previously had an admission for TSI rendering them eligible for inclusion in this study (regardless of whether they were included on the previous admission or not)

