### 3.4 Duration of Study

Local study teams may pick any 30-day period between the 6-month study period to conduct the study. Teams must follow patients for up to 6-weeks post-admission or until they are discharged or die (whichever event occurs first). For example, if a team selects 1/6/2021 as their start date, they must include all patients who meet the inclusion criteria between 1/6/2021 and 30/6/2021. Moreover, if a patient is admitted during the inclusion period on 30/6/2021 they should be followed up until the 11/8/2021 or until discharge or death (whichever event occurs first).

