#### Initial injury and admission data

- Baseline demographics e.g. age, gender
- Type and mechanism of injury
- Pre-hospital timeline, transfers and transportation
- Clinical presentation on arrival to hospital e.g. GCS, Kampala Trauma Score, Frankel grade
- Initial injury details
- Admission details

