### Outcome Data

Outcomes will be measured up to 6-weeks or until death/discharge (whichever event occurs first). This follow-up period was selected after consultation with experienced clinicians from high and low HDI settings to balance the aim of capturing significant short-term outcome events with practicalities of robust data collection across centres. This is supported by literature suggesting that over half of patients are typically lost to follow-up, with significantly increased barriers to follow-up in LMICs, and that early outcomes assessed within shorter time frames, particularly in these settings, remain significant and useful. A range of outcomes after traumatic spinal injury will be assessed including:

- Frankel grade at 6-weeks post-admission (or at discharge, whichever event occurs first). This has been demonstrated as a feasible measure to collect in both high and low resource settings.
- 6-week mortality
- Length of stay (LOS)
  - Hospital
  - Intensive Care Unit
- Perioperative complications (where applicable)
  - Return to operating theatre during follow-up period
  - Surgical site infection (SSI)
  - Adverse events of special interest e.g. pressure ulcer, pneumonia, deep venous thrombus
- Functional status at 6-weeks or discharge
  - Independence with activities of daily living
  - Mobility

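### Outcomes labelled as six-week stop at discharge or transfer, and sites may apply the entry rule differently to patients moved between participating hospitals

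*Combined protocol and SAP*

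**What the plan says.** **Follow-up and outcomes.** Section 3.4: "Teams must follow patients for up to 6-weeks post-admission or until they are discharged or die (whichever event occurs first". Section 3.5, Outcome Data, opens in the same way: "Outcomes will be measured up to 6-weeks or until death/discharge (whichever event occurs first". In the list beneath, the Frankel bullet repeats the discharge clause; the six-week mortality bullet does not. Section 5 gives the clause for trajectory, but the mixed model relating HDI to deterioration in function refers simply to six weeks.

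Appendix A 10.5 lists transfer to another hospital among the destinations of discharge. Its survival item runs to six weeks or discharge, whichever came first. Its death item asks about the six-week follow-up period and does not mention discharge.

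**Entry of transferred patients.** Section 3.1.2.1 requires "a first presentation of TSI confirmed radiographically". Section 3.1.2.2 excludes "Patients who have previously had an admission for TSI rendering them eligible for inclusion in this study", whether or not they were entered on that occasion. Section 3.5 nevertheless lists "Pre-hospital timeline, transfers and transportation" as study data, and Appendix A 10.1 records transport to the primary and the current institution separately. Primary, secondary and tertiary centres may all join (3.1.1), and Section 3.4 says: "Local study teams may pick any 30-day period between the 6-month study period to conduct the study".

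**The concern.** An outcome called six-week mortality will be read as the proportion dead at six weeks. What is collected is death before leaving the hospital, capped at six weeks. Patients who leave alive and die later inside the six weeks are recorded as survivors. How many there are depends on length of stay and on how often, and how early, a centre transfers patients. Those habits may differ between HDI groups, which is the comparison Section 5 makes, and Section 5 does not say how transferred patients enter it.

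The secondary matter is who enters a patient admitted at one participating hospital and moved to another. If sites answer differently, one injury can appear twice in pooled case-mix, outcomes and the incidence estimates.

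**Working it through.** **1. The plan's own figure.** Section 3.4 gives 11/8/2021 as the last follow-up date for an admission on 30/6/2021. 30/6/2021 + 42 days = 11/8/2021, so it reproduces. Six weeks is therefore a maximum length of follow-up, not a fixed assessment time.

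**2. One patient through the form.** Take a patient admitted on day 0, transferred out alive on day 4, and dead elsewhere on day 20. Discharge is yes, destination another hospital. The survival item is yes, because the patient survived to discharge. The death item is no if the follow-up period is taken to end at discharge, and yes if a site reads it as a fixed six weeks and learns of the death. The second reading is open because 10.5 asks about discharge as an event within that same six-week period.

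**3. Size of the mortality effect.** The documents give no rates; every input here is assumed.

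- Deaths missed after transfer, per 1,000 enrolled = 1,000 × share transferred × later mortality by six weeks. Low: 1,000 × 0.05 × 0.02 = 1. High: 1,000 × 0.20 × 0.10 = 20.
- Deaths missed after discharge home or to rehabilitation: 1,000 × 0.50 × 0 = 0 to 1,000 × 0.70 × 0.01 = 7.
- Effect on a comparison: recorded mortality = true mortality × (1 − share of deaths after exit). Two groups with the same true 10%, but 10% and 30% of deaths after exit, would record 10% × 0.90 = 9% and 10% × 0.70 = 7%. Which HDI group would be the lower is unknown.
- Dependence on stay: take a constant death hazard h and an exit-alive hazard d = 1/mean stay. Captured deaths = h/(h+d) × [1 − exp(−42(h+d))], with h = −ln(1 − M)/42 for true six-week mortality M. For M = 5% or 10%, the captured share is about 12%, 24%, 42–43% and 62% at mean stays of 5, 10, 20 and 40 days. Deaths probably cluster early, so these shares are likely lower bounds. They show only that capture varies with stay.

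**4. Size of possible double entry.** Assume 30-day windows placed independently and uniformly in 181–184 days, with transfer 0–3 days after admission. Enumeration gives a 0.181–0.184 chance that the second hospital's window is open on the transfer day; 0.18 is used. If a share t of patients is transferred, a share q of those goes to participating hospitals, and the second hospital enters them, x = t × q × 0.18 and the duplicate share of records is x/(1 + x).

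- Low: 0.05 × 0.25 × 0.18 = 0.00225, or 0.2%.
- High: 0.20 × 1.00 × 0.18 = 0.036, and 0.036/1.036 = 3.5%.
- If linked hospitals chose the same 30 days, the overlap is (30 − lag)/30 = 0.90–1.00, and the figures are about five times larger.

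**5. Could pairs be found?** Section 4.2 compares each site with its own validator only. Date of birth, gender and injury date/time are collected in 10.1. Expected chance pairs = (N × out) × (N × in) × P, for N = 1,000–5,000 records, 5–20% transferred out and 20–40% transferred in. With births spread over 50 years, 70% male (0.7² + 0.3² = 0.58) and injuries over 180 days, P = [1/(50 × 365.25)] × 0.58 × (1/180) = 1.76 × 10⁻⁷. That gives 0.002 to 0.35 pairs. If only the birth year is reliable, 1/50 replaces the first term and the range is 0.6 to 129. Flagged pairs therefore need review, not automatic linkage.

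**The case against.** **The truncation is declared.** The mortality bullet sits beneath a sentence ending outcome measurement at discharge. The objectives and Section 5 speak of early mortality, and the Section 5 paragraph containing the HDI model states the discharge clause for trajectory. Section 3.5 explains why short follow-up was chosen, and 10.5 collects dates of death and discharge, the destination, and inpatient status at six weeks. All of this stands: the cut-off is a reasoned choice, and transfers out are already identifiable and dated. It leaves untouched the bare labels, the open wording of the death item, and the silence on how transferred patients are analysed.

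**The eligibility text is coherent.** A reader might infer that 3.1.2.1, 3.1.2.2 and Appendix A 10.1 contradict one another. They do not. The first participating hospital where the patient is eligible enters them, the second excludes them, and the transport fields serve patients from non-participating hospitals or from hospitals whose window was closed. What stands is narrower. That reading is not written down, first presentation could mean first anywhere or first at that site, and the second hospital may not know whether the first takes part or when its window ran.

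A reader might also infer that the semi-elective exclusion ("patient initially discharged after emergency with planned intervention at a future date") catches patients sent on directly for surgery. That reading is strained: it works only by importing the form's discharge categories into an eligibility rule about planned later admissions.

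**Conclusion.** The outcome point holds. As collected, the measure is mortality to discharge, transfer or six weeks, whichever is first, and the function outcome stops at the same point. On the assumed rates, the deaths missed run from 1 to 20 per 1,000 after transfer and 0 to 7 per 1,000 after other discharge. A reader might infer that the HDI comparison is biased in a particular direction; the documents give no transfer or mortality rates from which to say so.

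The entry point is secondary: an ambiguity, not a contradiction, with duplicates of 0.2–3.5% of records under assumed rates and independent windows. That no cross-site check exists is also less than certain, because the scope of the ORION patient identifier is not stated and the flowchart is not shown.

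Nor does it follow that the receiving hospital ought to enter these patients. That would reverse a deliberate exclusion. It is a trade-off: entry at the first hospital only loses surgical detail from the second, since the 10.4 form opens only for surgery at the entering institution, and the primary objective covers care "including emergency, ward, surgical and ICU care"; entry at both creates duplicates.

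This should be fixed; confidence is medium.

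**What to change.** 1. **Labels.** In Sections 3.5 and 5, rename the outcomes as mortality to discharge/transfer or six weeks, whichever is first, and functional status at discharge/transfer, death or six weeks. Add the same clause to the death item in Appendix A 10.5.
2. **Analysis of transfers.** Using the discharge date and destination already collected, report transfer to another hospital as its own end state, not as alive at six weeks, and give its frequency by HDI group. Keep the Frankel grade at transfer as the planned observed value, and add a sensitivity analysis excluding patients transferred out.
3. **Entry rule and curation.** In Section 3.1.2, state one rule for direct transfers between participating hospitals; which rule is for the sponsor to decide. In central curation, flag likely cross-site pairs on date of birth, gender and injury date/time for review. Count confirmed pairs once for case-mix, outcome and incidence.

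**Cost.** Some rewording, a little extra analysis and no new data fields. The mortality label becomes less attractive. Some matches will be ambiguous, mainly where date of birth is inexact, and matching on it may prompt a local approval query because Section 7 promises that no identifiable data are collected. Deaths after transfer remain unobserved; the fix makes that visible but does not recover them.
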